### **The effect of application of ProAQT in guiding goal-directed hemodynamic therapy on postoperative recovery: A single-blind randomized controlled trial**

In both groups, intraoperative maintenance rate of crystalloid fluids is  $3 \text{ ml}\cdot\text{kg}^{-1}\cdot\text{hr}^{-1}$ . ProAQT-derived hemodynamic data are acquired at three time periods: before surgical incision, during OLV and at the end of surgery. Subjects randomized to the GDT group will be managed according to the ERAS algorithm utilizing ProAQT variables (mean arterial pressure, stroke volume variation and cardiac index) If stroke volume variation is  $\geq 10\%$ , a bolus of 150 ml of crystalloid fluid will be given until the stroke volume variation is  $< 10\%$ . If mean arterial pressure is  $< 70 \text{ mmHg}$  and/or cardiac index  $< 2.5 \text{ l}\cdot\text{min}^{-1}\cdot\text{m}^{-2}$  despite the stroke volume variation of  $< 10\%$  following fluid challenge, single or consecutive boluses of ephedrine 4 mg and/or continuous intravenous infusion of norepinephrine  $2\text{--}10 \text{ }\mu\text{g}\cdot\text{min}^{-1}$  will be administered. (Figure 1)

[figure not shown]

Figure 1: Goal-directed hemodynamic algorithm to guide intraoperative fluid therapy and the use of vasopressor and inotropic therapy in the goal-directed therapy group

Subjects allocated to the control group are hemodynamically managed as follows. Isolated hypotension (defined as 20% decrease in mean arterial pressure below baseline or < 60 mmHg) is treated by a continuous intravenous infusion of norepinephrine 2–10  $\mu\text{g}\cdot\text{min}^{-1}$ . If hypotension persists, repeat boluses of ephedrine 4 mg will be administered until mean arterial pressure is > 60 mmHg. If hypotension is accompanied by signs of hypovolemia (defined as urine output < 0.5  $\text{ml}\cdot\text{kg}^{-1}\cdot\text{hr}^{-1}$  and/or an increase in heart rate > 20% above baseline), crystalloid fluid will be administered until urine output and/or heart rate are normalized. Colloids are administered only when hypotension develops during acute hemorrhage. If hypotension persists despite volume challenges, norepinephrine will be administered. In both groups, fluid and inotrope or

vasopressor responsiveness and hemodynamic variables will be evaluated each 15 min, and more frequently in case of hemodynamic instability. ProAQT variables will be recorded every 15 min.

The primary outcome is in-hospital postoperative pulmonary complication, including atelectasis, pleural effusion, pneumonia, empyema, pulmonary embolism, re-operation, and respiratory failure. The diagnosis of atelectasis and pleural effusion will be made based on routinely performed chest radiographs on postoperative days 1 and 3. Pneumonia will be diagnosed if a patient presents with fever, leukocytosis and new infiltrates on chest radiography. Pleural empyema and pulmonary embolism will be confirmed by spiral computed tomography scan. Respiratory failure is defined as described. Secondary outcomes include relative change of PaO2/FiO2, PaO2/FiO2 values after induction of anesthesia and at the end of surgery, acute kidney injury (defined by Acute Kidney Injury Network Criteria), cardiac complications (myocardial infarction diagnosed by electrocardiogram and troponin T serum concentration; newly developed atrial fibrillation), clinically relevant hypotensive episodes (decrease in mean arterial pressure > 20% for more than 15 min requiring vasopressors), newly developed stroke, and length of hospital stay. All outcomes will be determined again 30 days after surgery and documented by research staff blinded to group allocation.

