### ***Statistical Analysis***

The distributions of baseline patient characteristics and outcome variables will be compared between two groups using chi-square tests or Fisher's exact test for categorical variables and either t tests or Wilcoxon rank sum tests for continuous variables, as appropriate. For time to event data, Kaplan-Meier method and log-rank test will be applied for group comparisons. Multivariable logistic regression, simple linear regression, or Cox proportional hazards regression analyses will be used to identify potential influential factors of outcomes of interest. A two-sided significance level of 0.05 was used to define statistically significant difference. All the statistical analyses will be conducted using Statistics Analysis System (SAS), Version 9.4 (SAS Institute Inc., Cary, NC, USA).

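### Does counting the ProAQT primary outcome only in hospital, with no stated role for the 30-day determination, undermine the comparison?

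*Combined protocol and SAP*

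**What the plan says.** The outcome paragraph of the ProAQT study in Section 5 defines the primary outcome: "The primary outcome is in-hospital postoperative pulmonary complication, including atelectasis, pleural effusion, pneumonia, empyema, pulmonary embolism, re-operation, and respiratory failure". Atelectasis and pleural effusion are diagnosed "based on routinely performed chest radiographs on postoperative days 1 and 3". Pneumonia, empyema and pulmonary embolism have diagnostic criteria but no assessment day. Re-operation has neither. Respiratory failure is defined by citation only.

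The secondary outcomes include "acute kidney injury (defined by Acute Kidney Injury Network Criteria"), "cardiac complications (myocardial infarction diagnosed by electrocardiogram and troponin T serum concentration; newly developed atrial fibrillation"), and "newly developed stroke, and length of hospital stay". The paragraph closes with: "All outcomes will be determined again 30 days after surgery and documented by research staff blinded to group allocation".

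The Statistical Analysis section compares outcome variables between groups with "chi-square tests or Fisher's exact test for categorical variables". It adds: "For time to event data, Kaplan-Meier method and log-rank test will be applied for group comparisons". It names no time point for any outcome and does not mention the 30-day determination.

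**The concern.** Two things look wrong.

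- **Unequal observation time.** For pneumonia, empyema, pulmonary embolism, re-operation and respiratory failure, hospital stay is the only stated window. If one arm goes home sooner for reasons unrelated to the lungs, it has fewer days in which an event can count. Equal true risks would then appear as a benefit for that arm. The plan lists length of stay as an outcome of this comparison, so it allows that stay may differ.
- **Two counts of one composite.** The in-hospital and 30-day counts will both exist, and the plan does not label the second. If the choice between them were made after seeing the data, the primary result would be open to selection.

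**Working it through.** The plan gives no sample size, power, event rate or length of stay, so there is no figure of its own to reproduce. The check has two parts: a reading of the text, and an illustration on assumed values.

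**Reading the text**

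1. Seven components are listed. Two have fixed film days (1 and 3), which leaves 7 − 2 = 5 whose only stated window is the hospital stay. Respiratory failure may carry a window in its cited definition, which cannot be checked here.
2. The primary outcome carries the label in-hospital in its own definition. The 30-day sentence says outcomes are determined *again*, which describes a second measurement beside the first and not a replacement.
3. Whether a patient had the composite is a yes/no variable. The chi-square or Fisher rule covers it at either time point. No time-to-event method or censoring rule is needed.

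**Illustration: assumptions**

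- R is the 30-day risk of the five clinical components, equal in both arms: 10%, 20% or 30%.
- f is the film-based risk, independent of R: 10%, 20% or 30%.
- In-hospital clinical risk for a stay of t days is either 1 − (1 − R)^(t/30) (constant hazard) or R(1 − e^(−t/4))/(1 − e^(−30/4)) (early onset, mean 4 days).
- Composite = 1 − (1 − f)(1 − clinical risk).
- False win for the shorter-stay arm = P(Z > 1.96 − difference/SE), with pooled SE and 2.5% nominal.

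**A. Stay differs only through kidney or cardiac events.** This route uses outcomes that the plan itself lists. Base stay is 5, 6 or 7 days. A share of each arm (10% vs 5%, or 20% vs 10%) stays 3, 5 or 7 days longer, so mean stay differs by 0.15 to 0.7 days. This gives 324 combinations.

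The largest case has R = 30%, f = 10%, base stay 5 days, 7 extra days, 20% vs 10%, constant hazard:

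- Clinical risk: 1 − 0.7^(5/30) = 5.77% at 5 days; 1 − 0.7^(12/30) = 13.30% at 12 days.
- Longer-stay arm: 0.2 × 13.30 + 0.8 × 5.77 = 7.28%; composite 1 − 0.9 × 0.9272 = 16.5%.
- Shorter-stay arm: 0.1 × 13.30 + 0.9 × 5.77 = 6.52%; composite 1 − 0.9 × 0.9348 = 15.9%.
- Difference 0.68 points. At 100 per arm SE = 5.21 points, so the false win is P(Z > 1.96 − 0.13) = 3.4%.

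Over all combinations the difference is 0.03 to 0.7 points (median 0.2), and the false win at 100 per arm is 2.5% to 3.4% (median 2.7%).

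**B. Whole arms differ in stay, cause unspecified.** Stays of 5 vs 4, 6 vs 5, 7 vs 6 or 7 vs 5 days give 72 combinations.

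| Quantity | Range | Median |
|---|---|---|
| False risk ratio | 0.88 to 0.99 | 0.97 |
| Difference, points | 0.2 to 3.0 | 0.8 |
| False win, 100 per arm | 2.7% to 6.8% | 3.4% |
| False win, 200 per arm | 2.8% to 9.7% | 3.9% |

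The false-win maxima need R = 30%, f = 10%, 7 vs 5 days and early onset: clinical risk 24.8% vs 21.4%, composite 32.3% vs 29.3%. With one-day differences the maxima are 5.3% and 7.1%.

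**C. Gap between the two counts when stay is equal (4 to 7 days).** The 30-day composite exceeds the in-hospital one by 1.2 to 9.9 points (median 3.8) with early onset, and by 5.3 to 22.8 points (median 12.8) with constant hazard. A longer window must contain at least as many events. The gap shows that the two counts answer different questions, not that either is wrong.

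**The case for a change.** The strongest case for a change does not depend on bias. All outcomes includes the primary one, so a reader could take the 30-day determination as extending or replacing the in-hospital count. Part C shows that the two can differ by several points even with early onset. One sentence naming the 30-day composite as a sensitivity result would settle this at almost no cost. Blinded documentation protects assessment; it does not equalise observation time.

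Much of that is fair. The label is missing, the counts are not interchangeable, and blinding does not answer the window question. It is also true that the plan does not say how discharged patients are assessed at day 30, or whether cumulative events or current status are recorded.

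What does not follow is that the planned comparison is unsound. The primary outcome is named as in-hospital, so reporting a 30-day count in its place would visibly depart from the protocol. The added sentence would record a use of data already planned and would leave the primary test exactly as it is. Making day 30 primary would change the test, but it would remove unequal follow-up in hospital at the price of possible incomplete capture after discharge. Reasonable statisticians would differ on that exchange.

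**Conclusion.** No change is called for. An in-hospital window is a legitimate choice for an intervention confined to the operation, with events verified by film, blood count and computed tomography. The unlabelled 30-day result is a gap that analysts would fill sensibly, by reporting it beside the in-hospital primary result.

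The bias needs discharge timing to differ by arm for reasons other than pulmonary complications; if stay differs only because of those complications, there is none. Through the kidney and cardiac route it is at most 0.7 points, with a false-win chance of at most 3.4% at 100 per arm. The larger values in part B need a whole-arm difference in stay that nothing in the documents leads one to expect. Listing length of stay as an outcome allows for a difference but does not predict one.

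All sizes rest on assumed risks, onset patterns, stays and arm sizes. A large observed difference in stay unrelated to pulmonary events would call for caution in reading the in-hospital result, and the planned 30-day data would then be available to examine it.

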### 4. Study Design

We will use the design of factorial parallel randomized controlled trial to conduct these two studies in the same patient group. A computer-generated list of randomizations (Research Randomizer, [www.randomizer.org](http://www.randomizer.org)) will be used for these group allocations. We will use stratified randomization method to ensure random allocations of these two treatments (spectral entropy and ProAQT goal-directed therapy) in all patients. Allocation will be concealed with sequentially numbered sealed opaque envelopes. The principal investigator will open the respective concealed envelope containing the patient allocation to the treatment arm on the day of surgery immediately before induction of anesthesia. In this trial, we will conform to the recommendations in the Consolidated Standards of Reporting Trials (CONSORT) statement. In addition, we will follow the principle of intention-to-treat in our analyses of the trial results.

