### 5. Study Methods

#### **The effect of M-Entropy guidance of anesthesia depth on postoperative recovery: A single-blind randomized controlled trial**

Standard monitoring will be applied, including five-lead electrocardiogram, pulse oximetry, capnography, radial artery catheterization for arterial blood pressure, and internal jugular vein cannulation for central venous pressure. Patients will be given balanced general anesthesia, including fentanyl 1–2  $\mu\text{g}\cdot\text{kg}^{-1}$  and propofol 1–2  $\text{mg}\cdot\text{kg}^{-1}$  for induction, and rocuronium 0.8  $\text{mg}\cdot\text{kg}^{-1}$  to facilitate tracheal intubation. Anesthesia will be maintained using sevoflurane 2–3 vol% in oxygen. An additional bolus of intravenous fentanyl 50  $\mu\text{g}$  will be administered before surgical incision. Pressure-controlled ventilation with a positive end expiratory pressure of 5 cm  $\text{H}_2\text{O}$  and peak pressure < 30 cm  $\text{H}_2\text{O}$  will be applied for both double-lung ventilation and OLV. OLV will be initiated after patients are in the lateral decubitus position. During double-lung ventilation the inspiratory oxygen fraction will be set to 0.6, whereas 0.8–1.0 will be used for OLV to ensure oxygen saturation higher than 92%. For double-lung ventilation, tidal volumes up to 8  $\text{ml}\cdot\text{kg}^{-1}$  and a respiratory rate of 10–15  $\text{min}^{-1}$  will be chosen, for OLV tidal volumes up to 6–7  $\text{ml}\cdot\text{kg}^{-1}$  with a respiratory frequency of 10–15  $\text{min}^{-1}$  will be used. In both groups re-inflating of the previously non-ventilated lung will be restarted by a manual recruitment maneuver with peak pressure 30 cm  $\text{H}_2\text{O}$  for 10 s three times. Intravenous parecoxib 40 mg will be given promptly after induction of anesthesia, followed by parecoxib 20 to 40 mg every 12 hours for three days.

Intravenous as-needed analgesia with morphine and/or ketorolac will be used to relieve breakthrough pain, which will be switched to oral diclofenac on the postoperative 2nd or 3rd day.

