In the M-Entropy group, dosage of volatile anesthetics will be adjusted to achieve the response and state entropy values between 40 and 60 from the start of anesthesia to the end of surgery. In the control group, dosage of volatile anesthetics will be titrated according to clinical judgment. This will be to maintain mean arterial pressure and heart rate within 20% range of the baseline. In case of signs of inadequate anesthesia (e.g. movement, cough and swallowing), anesthetic dose will be increased. M-Entropy monitoring will be continued in the control group, but the entropy number and EEG waveform will be concealed from the anesthetist in charge. Entropy values, hemodynamic, and expiratory gas data will be recorded in 5-min intervals. In all patients, cessation of general anesthesia will be timed to facilitate early awakening after wound closure. After reversal of the neuromuscular blocking agent and response to verbal command, all subjects will be extubated at the operating room and then transferred to the postanesthetic care unit. In the postoperative period, surgeons, medical and nursing staff at the postanesthetic care unit will be blinded to group allocation.

Primary outcome is time to spontaneous eye opening. Secondary outcomes include time to tracheal extubation, time to orientation in time and place, time to leave operating room, and events of emergence agitation, postoperative delirium, and intraoperative recall or awareness. We will use the Richmond Agitation-Sedation Scale to evaluate the level of agitation and sedation promptly after extubation. Events of delirium will be evaluated using the Confusion Assessment Method at the postanesthetic care unit 30 minutes after tracheal extubation. An independent adjudicator blinded to the group allocation will measure all the outcomes.

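### End-of-surgery PaO2/FiO2 is compared between arms without the post-induction value as a covariate, which usually costs some precision on this secondary outcome

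*Combined protocol and SAP*

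**What the plan says.** Section 5 of the combined protocol and SAP, in the ProAQT study, opens its list of secondary outcomes with "Secondary outcomes include relative change of" PaO2/FiO2, followed by the PaO2/FiO2 "values after induction of anesthesia and at the end of surgery". No formula for relative change is given.

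The Statistical Analysis section compares outcomes between two groups with "either t tests or Wilcoxon rank sum tests for continuous variables, as appropriate". It also names "Multivariable logistic regression, simple linear regression, or Cox proportional hazards regression analyses", but their stated purpose is to look for factors related to the outcomes, not to estimate the treatment effect. Linear regression appears only in its simple, one-predictor form. The significance level is 0.05 two-sided, and no multiplicity rule is given.

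Three statements bear on timing:
- Section 4 has the allocation envelope opened "on the day of surgery immediately before induction of anesthesia".
- The ProAQT study says "ProAQT-derived hemodynamic data are acquired at three time periods: before surgical incision, during OLV and at the end of surgery". It does not say when the algorithm first acts, or how the post-induction blood gas stands to that moment.
- In the M-Entropy study, titration of the volatile agent runs "from the start of anesthesia to the end of surgery".

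Figure 1, the hemodynamic algorithm, is not shown in the copy reviewed and may settle the timing.

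**The concern.** When the same quantity is measured early and late, regressing the late value on the early one and on treatment lets the data choose the weight given to the early value. The plan instead uses two fixed weights. The end value alone gives the early value no weight. Relative change, presumably a division by the early value, gives it a full proportional weight. The first does best when the samples are weakly correlated and the second when they are strongly correlated, and the plan cannot know beforehand which holds.

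At stake is the precision of one secondary comparison, from data that are already collected. Neither primary outcome (time to eye opening; pulmonary complications) is touched, and no planned test is invalid.

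**Working it through.** The plan states no mean, SD, correlation, effect or sample size for PaO2/FiO2, so there is no figure to reproduce and every input below is an assumption. Let x be the post-induction value, y the end value, r their correlation, and c = (mean of y × SD of x) / (mean of x × SD of y). Ratios are the variance of the treatment comparison relative to ANCOVA, and they describe comparisons of means, not the Wilcoxon option.

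**Formulas, large sample**
- End value: 1/(1 − r²).
- Relative change, first order: 1 + (c − r)²/(1 − r²).
- Power where ANCOVA has 80%: P(Z > 1.96 − 2.80/√ratio).

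Means of 400 and 350 with equal SDs give c = 350/400 = 0.875:

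| r | End value | Power | Relative change | Better of the two |
|---|---|---|---|---|
| 0.2 | 1.04 | 78% | 1.47 | 1.04 |
| 0.3 | 1.10 | 76% | 1.36 | 1.10 |
| 0.4 | 1.19 | 73% | 1.27 | 1.19 |
| 0.5 | 1.33 | 68% | 1.19 | 1.19 |
| 0.6 | 1.56 | 61% | 1.12 | 1.12 |
| 0.7 | 1.96 | 52% | 1.06 | 1.06 |

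**Worst case for the better of the two.** The two ratios are equal at r = c/2. For c = 0.75, 0.875 and 1 the ratio there is 1.16, 1.24 and 1.33, with power 74%, 71% and 68%. Over r = 0.2 to 0.7 the better of the two spans 1.00-1.16, 1.04-1.24 and 1.04-1.33 respectively.

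**Skewed data.** Lognormal values were simulated with post-induction mean 400, end mean 300-400, SD 60-120 and r = 0.2-0.7 on the log scale. The better planned comparison has ratio 0.80-1.30 against raw-scale ANCOVA, so relative change can be the more precise. Against log-scale ANCOVA with a proportional effect the ratio is 1.02-1.39.

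**Both tests together.** With 75 per arm assumed, means 400 and 350, SD 90 and no treatment effect, at least one of the two tests has p < 0.05 in 8.3-9.0% of trials (8.0-9.0% over 50, 75 and 150 per arm). With an effect for which ANCOVA has about 79% power, at least one is significant in 80-83% of trials. With a Bonferroni correction that falls to 70-74%.

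**Sampling time.** Take a true effect of 30 and equal SDs of 90. If goal-directed therapy has already shifted x by 20, the ANCOVA estimate should be about 30 − 20r, that is 26, 20 and 16 at r = 0.2, 0.5 and 0.7. Simulation gives 25.8, 20.1 and 15.8. If only the entropy arm shifts x by 20, and both factors are in the model, the goal-directed-therapy estimate stays at 30.2, 30.1 and 29.7.

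**The case against.** The strongest reply is that the plan already tests both the end value and relative change at 0.05, and an effect shows on at least one of them as often as ANCOVA would find it (80-83% against about 79%). That stands. A reader might infer that the plan is more likely to miss an oxygenation effect. The documents do not support this for the two tests read together; it holds only for a single test, or once the false-positive rate is controlled. The price of reading either test is the 8-9% error rate.

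A reader might also take 52% as the plan's power. That figure belongs to the end value alone at r = 0.7, where relative change is nearly as precise as ANCOVA (1.06), and the plan reports both.

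Nor does the text show that the post-induction sample is contaminated by goal-directed therapy. It leaves the timing open, and Figure 1 may resolve it. The same gap limits the remedy, because adjusting for a value already affected by treatment would bias a comparison that is now unbiased.

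Finally, the gain may be small. Section 5 plans different oxygen fractions by ventilation mode: "During double-lung ventilation the inspiratory oxygen fraction will be set to 0.6", and 0.8-1.0 on one lung. Neither blood gas is tied to a mode, and surgery lies between them, so a low r is plausible. At r = 0.2 the end value loses 4%; at r = 0, nothing. This keeps the point at low priority but does not remove it.

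**Conclusion.** The point holds as a matter of efficiency on one secondary outcome. No planned treatment comparison uses the post-induction PaO2/FiO2 as a covariate, and each planned comparison taken singly is usually less precise than an adjusted one. For assumed r = 0.2-0.7 the variance ratio is 1.04-1.96 for the end value and about 1.00-1.33 for the better of the two (c = 0.75-1, first order). The direction is not guaranteed: skewed data can favour relative change over raw-scale ANCOVA. The size rests wholly on assumed means, SDs and correlations. The case for adjusting also rests on the covariate preceding goal-directed therapy, which the visible text neither states nor contradicts. This is worth considering, with moderate confidence.

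**What to change.** Add to the Statistical Analysis section, as the between-arm analysis of the end value, a prespecified linear regression of end-of-surgery PaO2/FiO2 on post-induction PaO2/FiO2 and both randomised factors. Fix the scale (for example log) before unblinding, rather than choosing it from the data by arm. Interpret only the goal-directed-therapy term, because entropy titration starts with anesthesia and may already have affected the covariate. Keep relative change as listed.

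In the ProAQT outcome paragraph, state that the covariate sample is the one drawn before any algorithm-driven hemodynamic treatment. If that cannot be shown, keep the unadjusted end-value comparison and do not use the added model.

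The cost is one model and one sentence on sampling time. Both values are already collected and no listed outcome is removed. The downside is slightly more analysis work for a gain that may be small.

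### The secondary hypotension outcome requires vasopressor use, which the two arms' written rules trigger differently; for intraoperative episodes, part of the definition is therefore set by allocation

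*Combined protocol and SAP*

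**What the plan says.** All of the following is in section 5 (Study Methods) of the combined protocol and SAP, in the ProAQT part unless stated otherwise.

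- **Outcome.** The secondary outcomes include "clinically relevant hypotensive episodes (decrease in mean arterial pressure > 20% for more than 15 min requiring vasopressors". An episode must meet three conditions: depth, duration and a need for vasopressors. The plan does not say how need is judged, which period is covered, or when and how baseline MAP is measured.
- **Control arm.** "Isolated hypotension (defined as 20% decrease in mean arterial pressure below baseline or < 60 mmHg) is treated by a continuous intravenous infusion" of norepinephrine. If signs of hypovolemia accompany the hypotension, "crystalloid fluid will be administered until urine output and/or heart rate are normalized". After that, "If hypotension persists despite volume challenges, norepinephrine will be administered".
- **GDT arm.** When SVV is 10% or more, "a bolus of 150 ml of crystalloid fluid will be given until the stroke volume variation is" below 10%. If MAP is under 70 mmHg and/or cardiac index under 2.5 l/min/m² although SVV is below 10% "following fluid challenge, single or consecutive boluses of ephedrine 4 mg and/or continuous intravenous infusion of norepinephrine" follow. The prose refers to Figure 1, captioned "Goal-directed hemodynamic algorithm to guide intraoperative fluid therapy and the use of vasopressor and inotropic therapy in the goal-directed therapy group"; the figure is not shown in the text available.
- **Ascertainment.** "All outcomes will be determined again 30 days after surgery and documented by research staff blinded to group allocation".
- **Records.** The M-Entropy part plans a hemodynamic record every 5 min. The ProAQT part records the ProAQT variables, which include MAP, every 15 min.
- **Analysis.** The Statistical Analysis section compares categorical outcomes between the two groups by chi-square or Fisher's exact test.

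**The concern.** Two of the three conditions, depth and duration, describe the patient's blood pressure. The third describes what was done about it, and that is what the randomized strategies prescribe differently. The control trigger for isolated hypotension is the outcome's own 20% fall. The GDT trigger on MAP is an absolute 70 mmHg, with no rule in the prose tied to baseline.

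If the outcome covers the operation, a difference in event counts mixes two things: how often pressure stayed low, and how readily each arm's rule calls for a vasopressor. The planned two-group test cannot separate them, so neither a difference nor its absence could be read simply as a finding about hypotension. That matters because hypotension is one of the listed outcomes closest to what hemodynamic guidance acts on.

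**Working it through.** The plan gives no event rate, sample size or power for this outcome, so there is no figure to reproduce. The check applies the two written rules to the same blood pressure.

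**Inputs** (ProAQT part of section 5; B = baseline MAP, M = intraoperative MAP)

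- Outcome: M < 0.8B for more than 15 min, with vasopressors required.
- Control, isolated hypotension: vasopressor if M ≤ 0.8B or M < 60.
- GDT: vasopressor if SVV < 10% and (M < 70 and/or cardiac index < 2.5).

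**Step 1. Control rule against the outcome.** Any fall deep enough for the outcome (M < 0.8B) already meets the control trigger (M ≤ 0.8B), at every baseline. The 60 mmHg limit adds nothing for a qualifying fall.

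**Step 2. GDT rule against the outcome.** The 70 mmHg trigger coincides with a 20% fall when 0.8B = 70, so B = 70/0.8 = 87.5 mmHg. Above that baseline, MAP can be more than 20% down and still be 70 or higher. The two rules then disagree for M from 70 up to, but not including, 0.8B, given isolated hypotension, SVV < 10% and cardiac index ≥ 2.5.

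Band width = max(0, 0.8B − 70). Fall at which M reaches 70 = (B − 70)/B.

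| B (mmHg) | 0.8B | Band width (mmHg) | Fall at M = 70 |
|---|---|---|---|
| 85 | 68 | 0 | 17.6% |
| 87.5 | 70 | 0 | 20.0% |
| 90 | 72 | 2 | 22.2% |
| 95 | 76 | 6 | 26.3% |
| 100 | 80 | 10 | 30.0% |
| 110 | 88 | 18 | 36.4% |

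The band closes if cardiac index is below 2.5, because the GDT rule then also calls for a vasopressor.

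**Step 3. Example.** B = 95 and M stays at 73 for 20 min. The fall is (95 − 73)/95 = 23.2%, above 20%, and 20 min exceeds 15 min. With isolated hypotension the control rule calls for norepinephrine (73 < 76), so all three conditions are met. With SVV < 10% and cardiac index ≥ 2.5, the written GDT rule does not call for a vasopressor (73 ≥ 70), so the third is not met. The example assumes that M stays at 73 despite any treatment.

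**Step 4. Fluid-first steps.** These also differ, at any baseline. With SVV ≥ 10% and no signs of hypovolemia, GDT starts with fluid and control with norepinephrine. With signs of hypovolemia, SVV < 10% and a low MAP or cardiac index, control starts with fluid and GDT goes to a vasopressor (taking SVV < 10% as satisfying the fluid-challenge condition, an assumption). This changes the coding only if fluid alone corrects the episode after more than 15 min, which is a narrow case. The two patterns point in opposite directions.

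**Step 5. Resolution of the records.** Two consecutive readings 15 min apart span exactly 15 min, so three (2 × 15 = 30 min) are needed to show more than 15. With 5-min readings, five are enough (4 × 5 = 20 min). The choice of source therefore affects a threshold of more than 15 min.

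**The case against.** The strongest reply has five parts.

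- **No intraoperative window is stated.** Several neighbouring outcomes are postoperative, and all are determined again at 30 days. For postoperative episodes the intraoperative rules do not govern vasopressor use, and the mechanism disappears. This stands, and the point is conditional on it. A reader might infer that intraoperative episodes are certainly being coded by arm; the text does not go that far.
- **The same trace will rarely occur in both arms.** Control treats at a 20% fall precisely to raise MAP, so a control patient counts only if pressure stays low for over 15 min despite treatment, or if treatment is late. This also stands. Prompt treatment could remove control events, so a mismatch of rules need not become a mismatch of counts.
- **Figure 1 may contain a further GDT rule.** It may. The example is checked only against the prose.
- **Requiring may mean clinical need.** Possibly, but the plan gives no arm-neutral test of need. Its only written vasopressor criteria are the arm-specific ones. Blinded documentation does not help, because blinded staff would still be recording treatment that the arm's rule produced.
- **The trial compares strategies, so fewer vasopressor-treated episodes may be the intended effect.** That is a fair reason to keep the present measure. It does not make that measure interpretable as hypotension, and a MAP-only measure also reflects each arm's management.

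A reader might also tally the combinations of SVV, cardiac index and hypovolemia in which the arms' first steps differ, and take that as the size of the problem. It is not: the combinations are not equally likely, and the outcome depends on any vasopressor during the episode, not on the first step.

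**Conclusion.** The point holds in a limited form. As far as the outcome covers intraoperative episodes, its vasopressor condition is set partly by the assigned arm's written rule. The clearest case is a baseline MAP above 87.5 mmHg, with a discordant band 2 to 18 mmHg wide at baselines of 90 to 110 mmHg when hypotension is isolated, SVV is below 10% and cardiac index is at least 2.5.

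This assumes that the prose states the GDT rule in full, that requiring means use under the arm's rule, and that MAP stays low despite any treatment.

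A reader might infer a bias in favour of GDT, since the main example is an event in control only. The documents do not support that: the fluid-first steps can work the other way, and early control treatment may shorten episodes. Direction, size and frequency cannot be determined. Nor is the primary pulmonary outcome touched; only this secondary outcome is affected. This is a cheap improvement rather than a flaw in the trial's main conclusions.

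**What to change.** In the ProAQT outcome paragraph of section 5:

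1. State that the outcome covers the intraoperative period. If postoperative episodes are wanted, list them as a separate item with their own data source.
2. Define the episode identically in both arms as MAP more than 20% below baseline for more than 15 min, with no treatment condition.
3. Name the baseline as a MAP recorded before allocation is revealed, measured by the same method in both arms. Section 4 opens the envelope immediately before induction; section 5 plans a radial arterial line but does not say whether it is in place by then. This baseline is only the outcome's reference value.
4. State that the 5-min hemodynamic record in the M-Entropy part is the source, not the 15-min ProAQT record. Both comparisons use the same patients, so that record is already planned for everyone.
5. Report the present vasopressor-qualified definition beside the MAP-only one, and vasopressor use separately as a process measure.

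The cost is a reworded definition and a few added sentences, with no new data collection. The MAP-only version drops the severity qualifier, which reporting both versions keeps. It will still reflect each arm's management, but as a legitimate effect of the strategy on blood pressure. No change to either arm's treatment rule is proposed.
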